Power analysis. Using data from our preliminary study, a power analysis was run to estimate sample size for the outcomes of decreased A1C, improved cognitive function (i.e. working memory, executive function) using G*Power. For a fully powered randomized trial, assuming a small-to-moderate effect size of $d = .3$, each group would need 64 subjects for the power to be 0.8 at a 0.05 significance level. However, the proposed study is the first comparison test of the MAPSS-DM. A goal of this pilot study is to determine feasibility and to estimate effect sizes. Hertzog has shown that 10–20 subjects per group are often adequate for evaluating feasibility in a pilot study, and 30 subjects are needed when estimating effect sizes.⁴⁹ Allowing for a 10% attrition rate (based on PS#2), 66 persons with T2DM (33 intervention and 33 control) will be recruited.

Recruitment & Enrollment. Inclusion criteria: age 45-70 years old, T2DM diagnosis for 2 years, access to phone and Internet, Score of ≥ 10 on the Perceived Deficits Questionnaire (PDQ), and an A1C of $> 7\%$.⁵⁰ Exclusion criteria: a diagnosis of dementia/head injury, score of > 5 on the Mini-Cog, inability to speak English, and a T1DM diagnosis. For those who indicate interest in participating in the study, a screening assessment will be done either in person or by phone. A script of questions to verify that potential participants meet the inclusion/exclusion criteria will be followed. Participants will be asked the PDQ items that assess self-perceived cognitive difficulties, with questions such as "How often do you lose your train of thought when speaking?" using a 5-point scale ranging from 1 = never to 5 = almost always.⁵⁰ Potential participants must score at least 10 on the PDQ indicating some problems in at least 5 areas to participate. The Mini-Cog will screen potential participants for dementia.⁵¹ A total score of ≤ 5 indicates lower likelihood of dementia. For those who meet the inclusion criteria and agree to participate, a meeting will be scheduled at a time and private location convenient to the participant. Eligible participants will meet with a GRA or PI, who will review the study's purpose and procedures, answer participants' questions, obtain signed consent forms, and collect baseline data.

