Randomization. Seven cohorts of 10 subjects will be recruited during the study, and subjects in the cohort will be randomly assigned 1:1 to the intervention or control group using a computer-generated list of random numbers (following baseline testing). The intervention group will be further divided into class sizes of 10-5 participants. In prior cognitive rehabilitation studies, small intervention class sizes (n=10-12) enhanced self-efficacy through vicarious experience and modeling.⁵² In diabetes education, online groups of 10-15 participants have been shown to be effective.⁵²⁻⁵⁴

Data Collection. Questionnaire data will be collected from all participants on an iPad and entered into REDCap at baseline (week 0), at completion of the intervention (week 10), and at 3 months post-intervention (week 22). A GRA who is blind to group assignment will administer the instruments and neuropsych tests in a private location to ensure completion, confidentiality, and privacy. Clinical variables will be gathered by medical record review: current medications, past A1C levels, and co-morbidities. The total data collection time will be about 60 min. Participants will receive a small incentive (\$25) for completing the first two data collections and (\$50) for the final assessment (\$100 total). Data will be downloaded for analysis into IBM SPSS Statistics version 23.⁵⁵ All intervention participants will be invited to join a focus group after their final data collection to evaluate their perceptions of the acceptability of the MAPSS-DM intervention.

Table 1. Physiological Measures (pre- and post-intervention at week 2 and week 22)		
A1C	Medical record	The national standard measure of glycemic control over a 3-month period.
BMI	Weight, height	kg/m ²
Self-Report Measures (pre- and post-intervention) Time to Administer ~30 minutes for this battery		
Demographics	Background information	Age, gender, years with DM, ethnicity/race, socioeconomic status, history of DM education, years of education
DM-SM	Summary of Diabetes Self-Care Activities ⁵⁶	18 items; Participants answer "how many days in the last week..." they performed DM self-management such as diet and physical activity. Inter-item correlations range from $r = 0.20$ to 0.76 for four SDCA subscales; 4-month test-retest reliability range from $r = -0.05$ to 0.78 .

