Glucose Variability. Participants will wear CGMS devices for one week at specific intervals (week 0, week 5, week 11, and week 22). Abbott's FreeStyle Libre CGMS consists of a small, round sensor about the size of two stacked U.S. quarters—worn on the back of the upper arm for up to 14 days, which measures glucose every minute in interstitial fluid through a small (5mm long, 0.4mm wide) filament that is inserted just under the skin and held in place with a small adhesive pad.⁶² A reader is scanned over the sensor to get a glucose result painlessly in less than one second. Each scan displays a real-time glucose result, a historical trend and the direction the glucose is heading. Participants will scan the sensors at least 2 times a day. CGMS data will be downloaded at each data collection visit. The stored amperometric data from the monitor will be transferred and converted to glucose concentrations after data collection is completed using an infrared link to a personal computer and are analyzed using the CGMS solution software which will be maintained by the research staff. The FreeStyle Libre system generates an Ambulatory Glucose Profile (AGP) that provides a visual snapshot of glucose levels, trends and patterns over time. The following five glucose composites will be calculated: (1) the overall mean, (2) the proportion of readings indicating hypoglycemia (% <70mg/dL), (3) the proportion of readings indicating hyperglycemia (% >160mg/dL), (4) the proportion of out of range readings (% either <70mg/dL or >160mg/dL) and (5) the SD of CGM glucose readings.⁶³ Compared with SMBG, 85.5% of FreeStyle Libre readings were clinically accurate and 99.0% were clinically acceptable on a Clarke error grid, using linear mixed modelling.

Statistical significance. The data will be evaluated for violations of statistical tests. If assumptions are violated, alternative tests will be used or the data will be transformed. Individual t-tests will be run on the baseline variables (e.g. A1C, cognitive function tests) to determine if significant differences exist between the intervention and control groups, and we will control for those baseline differences in subsequent analyses. Analysis will follow intent-to-treat principles. Correlations will examine the relationships between the major variables. The significance level will be .05 for each test.

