Statistical Analyses. For Aim 1, we will use multilevel longitudinal models to estimate MAPSS-DM treatment effects on A1C, DM-SM and measurements of memory and executive function over time. Multilevel longitudinal models are generalizations of repeated-measures ANOVA that include every participant in the analysis, regardless of missing data, and will account for the clustering of measurements within participants. The model will also contain fixed effects for intervention (MAPSS-DM vs control) interacted with measurement occasion (baseline, 8 weeks, 3 months), as well as for cohort and baseline covariates. We will use the models to test for overall treatment effects ($p < 0.05$), effects at each post-baseline time-point, and within-subject effects. Effect sizes will be expressed as Cohen's d. Additionally, We will use causal-mediation methods and exploit the longitudinal structure of the data collection to estimate the mediational role of cognitive function. We will regress each cognitive function measurement at 8 weeks (post-intervention) on the group assignment (MAPSS-DM or control), the same cognitive measurement at baseline, and demographic controls.^{v&V2014} These regressions estimate the effect of the intervention on cognitive function at week 8. Next, we will regress the 3-month A1C and adherence measures at 3-months on the same variable at baseline, group assignment, cognitive measurements at week 8, and demographic controls. The average mediated effect of the intervention on A1C or adherence will be estimated by the sum of the coefficients on intervention from the first set of regressions multiplied by the coefficients on the corresponding cognitive measurements in the second regression, with Monte-Carlo confidence intervals and statistical tests.⁶⁴ For Aim 2, CGMS data will be downloaded at each data collection visit. Within subject change in the mean values of CGMS summary variables between pre-, during and post-intervention will be determined. The percentage of time spent in low

(<70mg/dL), normal (71mg/dL – 120mg/dL) and high (>160mg/dL) will be calculated. We will use analogous regression models to those in Aim 1 to estimate the effect of the intervention on glucose variability at post-baseline time-points, and mediational role of the of glucose variability in the intervention's effect on cognitive functions.

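### On the natural reading of the Aim 1 model, baseline covariates barely adjust the change-from-baseline treatment effect, and the plan does not say which treatment contrast it tests

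*Combined protocol and SAP*

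**What the plan says.** Under Statistical Analyses, the Aim 1 model for A1C, self-management and cognition has "fixed effects for intervention (MAPSS-DM vs control) interacted with measurement occasion (baseline, 8 weeks, 3 months), as well as for cohort and baseline covariates". Baseline is therefore one of the three response occasions. The model is used to "test for overall treatment effects ($p < 0.05$), effects at each post-baseline time-point, and within-subject effects"; none of these effects is written as a contrast. The plan notes that such models "include every participant in the analysis, regardless of missing data".

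Under Statistical significance, baseline variables, with A1C and the cognitive tests as examples, are compared between arms by t-tests. If they differ, "we will control for those baseline differences in subsequent analyses". Under Randomization, "subjects in the cohort will be randomly assigned 1:1 to the intervention or control group".

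The mediation regressions have a different form. The week-8 cognitive score is regressed on group, "the same cognitive measurement at baseline, and demographic controls", so there the baseline value is a covariate and not a response. Aim 2 uses models analogous to those of Aim 1.

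**The concern.** When baseline is a response and treatment is crossed with occasion, the usual treatment effect is the arm difference in change from baseline. A covariate with one coefficient shared by all occasions shifts the arm difference by the same amount at baseline and at each later visit. Subtracting baseline removes that shift.

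The covariate would then appear in the model, and the report could say that the imbalance was controlled, while the tested effect stayed essentially unadjusted. A chance imbalance on a variable that predicts change would pass into the estimate. The Power analysis section names effect-size estimation as a goal of this pilot, so an error of 0.1 to 0.3 SD would matter.

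**Working it through.** **Inputs.** From the documents: 33 per arm, seven cohorts, 10% attrition, three occasions, 0.05 per test. The plan gives no figure on this point to reproduce. Outcome SD, within-person correlation and covariate effects are not given; the values below are assumptions. Tests are taken as two-sided.

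**1. Algebra.** Write the mean of Y at occasion t as α_t + δ_t·G + γ·X, where G is arm and X a baseline covariate. Let D_t be the raw arm difference at occasion t and ΔX the arm difference in X. With complete data and any common within-person covariance:

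- arm difference at a visit: δ̂_t = D_t − γ̂·ΔX
- change contrast: δ̂_t − δ̂_0 = D_t − D_0, from which γ̂ has vanished
- with a slope for each occasion: δ̂_t − δ̂_0 = (D_t − D_0) − (γ̂_t − γ̂_0)·ΔX

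The third form is the one that adjusts the change contrast.

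**2. Numerical check, complete data.** In 500 simulated trials per covariance structure (66 participants, seven cohorts), adding cohort and one covariate as main effects moved the change contrasts by at most 2e-15 and their standard errors by at most 6e-17. This held under compound symmetry and under an unstructured matrix. Using the outcome's own baseline as the covariate (compound symmetry) also left the contrasts unchanged.

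**3. With 10% dropout.** The cancellation is no longer exact. The mean absolute shift was 0.010 to 0.020 and the largest 0.04 to 0.11, against a standard error of about 0.23 to 0.33.

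**4. Error left in the contrast.** Assume an imbalance of 0.4 SD and covariate slopes of 0.5, 0.7 and 0.8 at the three occasions. By step 1 the error is (0.7 − 0.5) × 0.4 = 0.08 at the first post-baseline visit and (0.8 − 0.5) × 0.4 = 0.12 at the last. With complete data the simulated error at the last visit was 0.11 to 0.12 with main effects and about 0 with covariate-by-occasion terms.

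**5. Error rate when the plan's trigger fires.** Given |z| > 1.96 for the baseline difference, the mean |z| is 2φ(1.96)/0.05 = 2 × 0.0584/0.05 = 2.34. The imbalance is then about 2.34 × √(2/33) = 0.576 SD. If the covariate correlates r with change, the change contrast's z has mean about 2.34r and SD √(1 − r²) under no treatment effect.

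| r (assumed) | Error, SD of change (0.576r) | Mean of z | SD of z | P(abs. z > 1.96) | Simulated |
|---|---|---|---|---|---|
| 0.3 | 0.17 | 0.70 | 0.954 | 9.6% | 9.5% |
| 0.4 | 0.23 | 0.94 | 0.917 | 13% | 13.3% |
| 0.5 | 0.29 | 1.17 | 0.866 | 18% | 18.4% |

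The simulated rates rest on about 15,000 triggered trials per row. Over all trials, triggered or not, the rates were 4.9%, 5.0% and 4.9%. With covariate-by-occasion terms the rate in triggered trials was about 5–6%.

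**6. The outcome's own baseline.** With equal variances and within-person correlation ρ, baseline correlates −√((1 − ρ)/2) with change: −0.50 at ρ = 0.5 and −0.32 at ρ = 0.8. These lie within the range of step 5 in size. In trials with a significant baseline difference, the change contrast had simulated false-positive rates of 18%, 15%, 12% and 11% for ρ = 0.5, 0.6, 0.7 and 0.8, against 5–6% for ANCOVA.

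**7. The other contrast.** In the scenarios of steps 2 and 3, main effects moved the arm difference at each visit, and its average over visits, by about 0.25 to 0.27. If the outcome's own baseline is both covariate and response, its slope depends on the covariance model. Under exchangeable covariance it is (1 + 2ρ)/3, which is 0.73 at ρ = 0.6 rather than 0.60. Other structures give other values, and the plan names none.

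**The case against.** - **Main effects are inferred.** The model sentence is a summary and does not exclude covariate-by-occasion terms. This stands as a caveat. But the sentence crosses only intervention with occasion, and the plan asks for interaction terms explicitly elsewhere (group by sex, under Potential sources of biological variation).
- **A reader might infer that the covariates cancel exactly, or that adjustment does nothing.** The documents support neither. Exact cancellation needs complete data, and this plan expects attrition and keeps participants with missing visits. Main effects do adjust a per-visit or averaged arm difference, which the undefined effects could mean.
- **A reader might infer an inflated type I error.** It is not inflated overall: randomization holds it at 5%. The higher rates apply only after a significant baseline t-test, about 5% of trials for any one covariate.
- **Baseline outcome differences are already subtracted.** They are, but with slope 1 as in a change score, which ignores regression to the mean (step 6).
- **The mediation regressions use ANCOVA.** They do, so part of the promised control is delivered there. The Aim 1 treatment-effect model and its Aim 2 counterparts do not share that form.
- **Cohort.** Assignment is 1:1 within cohort, so there is no bias to correct. Only precision is at issue.

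**Conclusion.** The concern holds for the treatment-by-occasion contrast, on the natural main-effects reading. For that contrast the promised control for baseline differences is absent with complete data and negligible at about 10% dropout. The plan also leaves open whether that contrast or a per-visit arm difference is tested, and the two are adjusted very differently by the same model.

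When the plan's own trigger fires, the estimate is off by about 0.17 to 0.29 SD of change. The false-positive rate is about 9–10%, 13% or 18% for assumed covariate–change correlations of 0.3, 0.4 or 0.5. The documents give no such correlation, and a covariate unrelated to change would leave no error. The point is therefore a specification gap that should be closed before analysis. It does not show that the trial's test is invalid.

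**What to change.** In the SAP:

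1. Define the treatment effect as the arm difference in change from baseline at each post-baseline visit, and define the overall effect as a stated combination or joint test of these.
2. Enter each retained baseline covariate with its interaction with occasion, in the Aim 1 models and the analogous Aim 2 models.
3. Never use the modelled outcome's own baseline as both covariate and response. Either model post-baseline rows only with baseline, by occasion, as covariate (as the mediation regressions already adjust), or keep baseline as a response with means constrained equal across arms. The second option also retains participants with no post-baseline visit, in line with the plan's wish to keep everyone.
4. Cohort-by-occasion is optional.

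The cost is wording plus 2 df per covariate with three occasions (3 df if all four Aim 2 sensor weeks are response occasions). Cohort-by-occasion would add 6 × 2 = 12 df. No change to data collection or sample size is needed.

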Self-efficacy	Diabetes Empowerment Scale – Short Form ⁵⁷	8 items; Brief assessment of diabetes related psychosocial self-efficacy. Responses are made on a 5-point scale (1 = strongly disagree to 4 = strongly agree) to items such as "I believe that I am able to turn my diabetes goals into a workable plan." Cronbach's alphas range from 0.81 to 0.96.
Depression	CES-D ⁵⁸	20 items; measures depressive symptoms. 4-point item response scale from rarely/none of the time to most/all of the time in 8 health dimensions: role limitations due to physical problems, social functioning, physical functioning, bodily pain, general mental health, role limitations due to emotional problems, vitality, and general health perceptions. Internal consistency ranged from 0.85 to 0.91 and test-retest reliability ranged from 0.45 to 0.70.
Perceived Cognitive Function	PROMIS v2.0 – Cognitive Function ⁵⁹	32 items; assess patient-perceived cognitive deficits including the areas of mental acuity, concentration, verbal and nonverbal memory, and verbal fluency. Reliability has been measured at 0.94 and test-retest correlation at 0.83. (Becker 2014)
Objective Cognitive Function Measures (pre- and post-intervention) ~ 35 minutes to administer		
Episodic memory	Picture Sequence Memory (NIH-Toolbox) ⁶⁰	Assessment of episodic memory. It involves recalling increasingly lengthy series of illustrated objects and activities presented in a particular order on the computer screen. Participants are asked to recall the sequence of pictures demonstrated over two learning trials. Participants are given credit for each adjacent pair of pictures (i.e., if pictures in locations 7 and 8 and placed in that order and adjacent to each other anywhere – such as slots 1 and 2 – one point is awarded) they correctly place, up to the maximum value for the sequence, which is one less than the sequence length (if there are 18 pictures in the sequence, the maximum score is 17, because that is the number of adjacent pairs of pictures that exist).

Executive Function and Attention	Flanker Inhibitory Control and Attention (NIH-Toolbox) ⁶⁰	Measures both a participant's attention and inhibitory control. The test requires the participant to focus on a given stimulus while inhibiting attention to flanking it. Scoring is based on a combination of accuracy and reaction time.

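### The mediation regressions name no baseline depression, co-morbidity or medication covariate, so the cognition-to-outcome path can be confounded even when the arms are balanced

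*Combined protocol and SAP*

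**What the plan says.** The Statistical Analyses section writes out two regressions for the Aim 1 mediation analysis.

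- **Mediator model.** Each post-intervention cognitive measure (labelled week 8) is regressed on group, "the same cognitive measurement at baseline, and demographic controls".
- **Outcome model.** Three-month A1C or adherence is regressed "on the same variable at baseline, group assignment, cognitive measurements at week 8, and demographic controls".

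The mediated effect is the sum, over cognitive measures, of the group coefficients "multiplied by the coefficients on the corresponding cognitive measurements in the second regression, with Monte-Carlo confidence intervals and statistical tests". For Aim 2 the plan states: "We will use analogous regression models to those in Aim 1".

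The main longitudinal model has wider adjustment, "as well as for cohort and baseline covariates", but the baseline covariates are not listed and the phrase is not repeated for the mediation regressions.

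The candidate covariates are recorded. Table 1 includes the CES-D ("20 items; measures depressive symptoms") in the self-report battery given before and after the intervention. The Data Collection section adds: "Clinical variables will be gathered by medical record review: current medications, past A1C levels, and co-morbidities". The demographics row of Table 1 has seven items. Two of these relate to the disease (years with diabetes and previous diabetes education), but none is depression, co-morbidity or medication.

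The Statistical significance section tests baseline variables between arms and, where they differ, says "we will control for those baseline differences in subsequent analyses".

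**The concern.** The mediated effect is a product of two coefficients. Randomization protects the first, from group to cognition. It does not protect the second, from cognition to outcome, because nobody is randomized to a level of post-intervention cognition. The second coefficient is causal only if the common causes of cognition and later A1C or self-management are in the model.

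Depressive symptoms, co-morbidity and medication are plausible common causes. A participant with more depressive symptoms may score worse on testing and also manage diabetes less well. The outcome model would then credit that association to cognition, and it would be reported as the mechanism by which MAPSS-DM works. The plan calls this a causal-mediation analysis, yet it states no assumption about unmeasured confounding and plans no sensitivity analysis for it. A mistaken mechanism could also steer the design of the fully powered trial.

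**Working it through.** The plan gives no figure for the mediation analysis, so there is none to reproduce. The check is a comparison of the covariates, followed by illustrations on stated assumptions.

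**1. Covariates named**

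| Term | Main Aim 1 model | Mediator model | Outcome model |
|---|---|---|---|
| Group | yes | yes | yes |
| Baseline value of the dependent variable | yes (baseline is a measurement occasion) | yes | yes |
| Demographics | possibly (baseline covariates unlisted) | yes | yes |
| Cohort | yes, fixed effect | not named | not named |
| CES-D, co-morbidity, medication | possibly (baseline covariates unlisted) | not named | not named |
| Baseline cognition | not applicable | yes | not named |

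**2. Bias in the cognition coefficient**

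With one mediator and one omitted confounder in SD units, bias = (correlation of confounder with week-8 cognition) × (effect of confounder on outcome). Both are read as what remains after the covariates already in the model. The strengths below are assumed.

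| Correlation | Effect (SD) | Bias (SD per SD) |
|---|---|---|
| −0.2 | 0.1 | −0.02 |
| −0.3 | 0.2 | −0.06 |
| −0.4 | 0.3 | −0.12 |

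If the true coefficient is zero, with an assumed residual variance of 0.75 and 52 residual degrees of freedom, SE = √(0.75/52) = 0.12. A 5% two-sided test of that coefficient then rejects in about 5% of trials at the weakest setting and 17% at the strongest (0.12/0.12 = 1.0 SE of bias). With 44 degrees of freedom, as in step 5, SE = √(0.75/44) = 0.13 and the upper figure is about 15%.

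**3. The quantity the plan reports is the product**

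With a group effect on cognition of 0.3 SD (the d in the Power analysis section), the false mediated effect is at most 0.3 × 0.12 = 0.036 SD. A one-mediator simulation used 60 participants, no true cognition effect, the strengths in step 2 and assumed autocorrelations of 0.7 (cognition) and 0.5 (outcome). The Monte-Carlo interval for the product excluded zero in about 2%, 3% and 5% of runs at a group effect of 0.3 SD, and about 4%, 6% and 12% at 0.5 SD.

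**4. Does the baseline outcome already deal with it?**

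A second simulation let one baseline factor act, with path c, on cognition and on the outcome, at baseline and again at follow-up. Carry-over from baseline was 0.6 and the true cognition effect was zero. The planned models were fitted, including the baseline outcome.

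| Path c | Cognition coefficient (true 0) | False mediated effect, group effect 0.5 | Coefficient test rejects, n = 60 | Product interval excludes 0, group effect 0.5 / 0.8 |
|---|---|---|---|---|
| 0.1 | −0.02 | −0.01 | 6% | 4% / 6% |
| 0.2 | −0.07 | −0.03 | 11% | 7% / 11% |
| 0.3 | −0.13 | −0.06 | 25% | 16% / 26% |
| 0.4 | −0.19 | −0.09 | 49% | 30% / 48% |

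Bias remains despite the baseline-outcome term. Adding the factor and baseline cognition returned the coefficient to 0.00 and its test to 5%. Adding baseline cognition alone did not remove the bias. At a group effect of 0.5 the product rejects less often than the coefficient; at 0.8 the two rates are about equal.

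**5. Cost in degrees of freedom**

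Completers: 66 × 0.9 = 59.4, about 59. Outcome-model parameters, with five objective cognitive measures and one term per demographic item: 1 + 1 + 1 + 5 + 7 = 15, leaving 44.

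| Added terms | Residual df | SE factor if uninformative |
|---|---|---|
| 3 covariates | 41 | √(44/41) = 1.04 |
| 3 covariates + 6 cohort terms | 35 | √(44/35) = 1.12 |
| 3 covariates + 5 baseline cognitive measures | 36 | √(44/36) = 1.11 |
| all of these | 30 | √(44/30) = 1.21 |

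These factors count degrees of freedom only. Baseline cognition is also correlated with week-8 cognition, which widens the coefficient's SE further. At an assumed correlation of 0.7 the extra factor for a single measure is √(1/(1 − 0.49)) = 1.40.

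**6. The imbalance rule**

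Under sound randomization a given baseline variable is flagged 5% of the time; for any of three independent variables, 1 − 0.95³ = 14%. A mediator-outcome confounder biases the second path whether or not it is flagged.

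**The case against.** Several points on the other side stand.

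- The regressions do not control for demographics alone. Each adjusts for the baseline value of its own dependent variable, and baseline A1C or adherence absorbs part of any stable influence of depression, co-morbidity or medication. This is a real safeguard, but a partial one (step 4).
- A reader might infer that CES-D and the clinical variables enter no analysis at all. The documents do not support that. The main model's baseline covariates are unlisted, correlations among the major variables are planned, and the imbalance rule could bring any of them in. What the text supports is that they are not named in any analysis.
- A reader might take 5% to 17% as the rate of false mediation claims. It is the rate for the cognition coefficient. The product estimate is significant less often unless the group effect on cognition is large.
- Every strength used above is assumed, and the plan enters several cognitive measures jointly, whereas the illustrations use one.
- Cohort is a weak confounder. The case for including it is consistency with the main model.
- This is a pilot for feasibility and effect sizes, mediation is an additional analysis, and with about 59 completers the choice of covariates is partly judgement. That argues for a short list. It does not justify leaving the choice to arm balance, and a small sample does not reduce bias.

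**Conclusion.** The point holds as a limited gap in specification. Followed as written, the mediation regressions leave out recorded variables that may be common causes of cognition and outcome, and neither the baseline-outcome term nor the imbalance rule closes the gap. Aim 2 inherits it by analogy.

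The actual bias cannot be computed from the documents. For one confounder at the assumed strengths in step 2, it is about 0.02 to 0.12 SD per SD in the cognition coefficient; stronger paths give more. The documents do not show that the planned mediation result will be wrong, nor do they cast doubt on the randomized comparisons: the estimates of treatment effect on A1C, self-management and cognition are unaffected. This is a worthwhile, inexpensive improvement to a secondary causal analysis.

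**What to change.** In the Statistical Analyses section:

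1. Name three covariates for both Aim 1 mediation regressions and the analogous Aim 2 models, included regardless of arm balance: baseline CES-D score, a baseline co-morbidity count, and one baseline diabetes-medication indicator.
2. Use pre-randomization values only, since later mood or medication may be affected by treatment. The record review is undated in the Data Collection section, so state the reference date.
3. Add the baseline cognitive measure to the outcome regression (in Aim 2, the baseline value of the glucose mediator). It is a pre-treatment common cause of later cognition and self-management. It complements the three covariates and does not replace them.
4. Treat cohort as optional; if used, enter it as a fixed effect, as in the main model.
5. State the no-unmeasured-confounding assumption and, preferably, a simple sensitivity analysis for it.

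The change is to wording and uses data already collected. The three covariates cost about 3 degrees of freedom and about 4% in SE if they explain nothing, and less if they are prognostic. Each baseline cognitive measure costs one more degree of freedom and some precision through its correlation with the week-8 measure. Cohort costs about six degrees of freedom. If precision is the constraint, pre-specify fewer cognitive mediators rather than dropping the confounders.
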